Appendix 7: Grading Scale for Adverse Events Related to Laboratory Abnormalities

Adverse Event	Mild	Moderate	Severe
Cardiac troponin T increased	Levels above the upper limit of normal and below the level of myocardial infarction as defined by the manufacturer	-	Levels consistent with myocardial infarction as defined by the manufacturer
CD4 lymphocytes decreased	<LLN - 500/mm ³ ; <LLN - 0.5 x 10 ⁹ /L	<500 - 200/mm ³ ; <0.5 - 0.2 x 10 ⁹ /L	<200/mm ³ ; <0.2 x 10 ⁹ /L
CPK increased*	>ULN - <6 ULN	6 - 10 x ULN	>10 x ULN
Creatinine increased	>1 - 1.5 x baseline; >ULN - 1.5 x ULN	>1.5 - 3.0 x baseline; >1.5 - 3.0 x ULN	>3.0 x baseline; >3.0 x ULN
GGT increased	>ULN - 2.5 x ULN	>2.5 - 5.0 x ULN	>5.0 x ULN
Hypercalcemia	Corrected serum calcium of >ULN - 11.5 mg/dL; >ULN - 2.9 mmol/L; Ionized calcium >ULN - 1.5 mmol/L	Corrected serum calcium of >11.5 - 12.5 mg/dL; >2.9 - 3.1 mmol/L; Ionized calcium >1.5 - 1.6 mmol/L; symptomatic	Corrected serum calcium of >12.5 mg/dL; >3.1 mmol/L; Ionized calcium >1.6 mmol/L; hospitalization indicated
Hyperglycemia	Fasting glucose value >ULN - 160 mg/dL; Fasting glucose value >ULN - 8.9 mmol/L	Fasting glucose value >160 - 250 mg/dL; Fasting glucose value >8.9 - 13.9 mmol/L	>250 mg/dL; >13.9 mmol/L; hospitalization indicated
Hyperkalemia	>ULN - 5.5 mmol/L	>5.5 - 6.0 mmol/L	>6.0; hospitalization indicated
Hypermagnesemia	>ULN - 3.0 mg/dL; >ULN - 1.23 mmol/L	-	>3.0 mg/dL; >1.23 mmol/L
Hypernatremia	>ULN - 150 mmol/L	>150 - 155 mmol/L	>155 mmol/L; hospitalization indicated
Hyperuricemia	>ULN - 10 mg/dL (0.59 mmol/L) without physiologic consequences	-	>ULN - 10 mg/dL (0.59 mmol/L) with physiologic consequences
Hypoalbuminemia	<LLN - 3 g/dL; <LLN - 30 g/L	<3 - 2 g/dL; <30 - 20 g/L	<2 g/dL; <20 g/L
Hypocalcemia	Corrected serum calcium of <LLN - 8.0 mg/dL; <LLN - 2.0 mmol/L; Ionized calcium <LLN - 1.0 mmol/L	Corrected serum calcium of <8.0 - 7.0 mg/dL; <2.0 - 1.75 mmol/L; Ionized calcium <1.0 - 0.9 mmol/L; symptomatic	Corrected serum calcium of <7.0 mg/dL; <1.75 mmol/L; Ionized calcium <0.9 mmol/L; hospitalization indicated
Hypoglycemia	<LLN - 55 mg/dL; <LLN - 3.0 mmol/L	<55 mg/dL; <3.0 mmol/L	<40 mg/dL (<2.2 mmol/L) AND requires assistance of another person to actively administer carbohydrates, glucagon, or take other corrective actions ^t
Hypokalemia	<LLN - 3.0 mmol/L	<LLN - 3.0 mmol/L; symptomatic; intervention indicated	<3.0 mmol/L; hospitalization indicated
Hypomagnesemia	<LLN - 1.2 mg/dL; <LLN - 0.5 mmol/L	<1.2 - 0.9 mg/dL; <0.5 - 0.4 mmol/L	<0.9 mg/dL; <0.4 mmol/L
Hyponatremia	<LLN - 130 mmol/L	-	<130 mmol/L
Hypophosphatemia	<LLN - 2.5 mg/dL; <LLN - 0.8 mmol/L	<2.5 - 2.0 mg/dL; <0.8 - 0.6 mmol/L	<2.0 mg/dL; <0.6 mmol/L
Lipase increased	>ULN - 1.5 x ULN	>1.5 - 2.0 x ULN	>2.0 x ULN
Serum amylase increased	>ULN - 1.5 x ULN	>1.5 - 2.0 x ULN	>2.0 x ULN

Appendix 7: Grading Scale for Adverse Events Related to Laboratory Abnormalities

Adverse Event	Mild	Moderate	Severe
Urine			
Proteinuria			
Adults	1+ proteinuria; urinary protein <1.0 g/24 hrs	2+ proteinuria; urinary protein 1.0 - 3.4 g/24 hrs; Urine P/C (Protein/Creatinine) ratio 0.5 - 1.9	Urinary protein ≥3.5 g/24 hrs; Urine P/C >1.9
Children	-		
Hematuria	Asymptomatic; clinical or diagnostic observations only; intervention not indicated	Symptomatic; urinary catheter or bladder irrigation indicated	Gross hematuria; transfusion, IV medications or hospitalization indicated; elective endoscopic, radiologic or operative intervention indicated

¹Grading for this parameter is derived from the Toxicity Grading Scale for Healthy Adult and Adolescent Volunteers Enrolled in Preventive Vaccine Clinical Trials, Sept 2007

*Grading for this parameter is derived from the Division of AIDS (DAIDS) Table for Grading the Severity of Adult and Pediatric Adverse Events Version 2.0, Nov 2014

²Modified for consistency with the ADA and Endocrine Society Guidelines (Sequist ER, Anderson J, Childs B, et al. Hypoglycemia and Diabetes: A Report of a Workgroup of the American Diabetes Association and The Endocrine Society. Diabetes Care 2013;36:1384-95)

4.8.1.4	Clinical Global Impression-Change	18
4.8.1.5	Montreal Cognitive Assessment	18
4.8.1.6	Summary of outputs for describing the parameters over time.....	19
4.8.2	Relationship between selected parameters	19
4.9	Pharmacokinetic and PKPD Analyses.....	21
4.10	Interim Analyses	22
	REFERENCES	23

LIST OF TABLES

Table 1. CSF Safety Labs Standard (Marked) Reference Ranges	11
Table 2. Vital Signs (Supine) Abnormality Ranges	11
Table 3. ECG Parameters Abnormality Ranges	12
Table 4. Criteria for abnormal absolute QTc and change in QTcF interval	12
Table 5. Overview of planned outputs to describe parameter evolution over time	19
Table 6. Overview of planned outputs to describe the association between selected pairs of parameters	20

LIST OF FIGURES

Figure 1. Diagram of study design	3
---	---

STUDY GLOSSARY

Abbreviation	Definition
ADA	Anti-drug antibody
ALT	Alanine aminotransferase
aPTT	Activated partial thromboplastin time
ASO	Antisense oligonucleotide
AST	Aspartate aminotransferase
AUC	Area under the plasma concentration-time curve
BLQ	Below the limit of quantification
CAG	Cytosine, adenine, guanine base sequence found in DNA which is translated into glutamine
CAP	CAG age product
CGI-C	Clinical Global Impression – Change
CGI-S	Clinical Global Impression – Severity
ClinRO	Clinician-reported outcome
CNS	Central nervous system
CSF	Cerebrospinal fluid
C-SSRS	Columbia-Suicide Severity Rating Scale
DNA	Deoxyribonucleic acid
EC	Ethics Committee
ECG	Electrocardiogram
eCRF	Electronic Case Report Form
EDC	Electronic data capture
FDA	Food and Drug Administration
HA	Health Authorities
HD	Huntington's disease
HD-DAS	Huntington's Disease -Daily Activities Scale
HTT	Huntingtin gene
IMP	Investigational medicinal product
INR	International normalized ratio
IRB	Institutional Review Board
IT	Intrathecal
MAD	Multiple ascending dose
MedDRA	Medical Dictionary for Regulatory Activities
mHTT	Mutant Huntingtin
MoCA	Montreal Cognitive Assessment

MOE	Methoxyethyl
mRNA	Messenger ribonucleic acid
NfL	Neurofilament light chain
OLE	Open-label extension
PD	Pharmacodynamics(s)
PerfO	Performance outcome
PK	Pharmacokinetic(s)
PT	Prothrombin time
QTc	Corrected QT interval
QTcF	QT interval corrected through use of Fridericia's formula
RBC	Red blood cell
RBR	Research Biosample Repository
RNA	Ribonucleic acid
SAP	Statistical Analysis Plan
SDMT	Symbol Digit Modalities Test
SI	Système International d'Unités
SPA	Statistical Programming & Analysis
SWRT	Stroop Word Reading Test
Study Day 1	Defined as the first day Study Drug is administered to the patient
Study Drug	RO7234292 (previously known as ISIS 443139)
TEAE	Treatment-emergent adverse event
TFC	Total Functional Capacity
TMS	Total Motor Scale
UHDRS	Unified Huntington's Disease Rating Scale
ULN	Upper limit of normal
WBC	White blood cell
WES	Whole exome sequencing
WGS	Whole genome sequencing
wtHTT	Wild-type huntingtin

1. BACKGROUND

This Statistical Analysis Plan describes all planned methods of summarizing and analyzing data to be collected in study BP40410. Study BP40410 is an open-label, adaptive multiple-dose clinical study designed to generate time course data on PK, PD, and the PK/PD relationship after intrathecal (IT) administration of RO7234292 to patients with manifest HD (males and females aged 25-65 years, inclusive).

Huntington's disease is an autosomal dominant neurodegenerative disease caused by a CAG repeat expansion in the first exon of the HTT gene located on Chromosome 4 resulting in a polyglutamine expansion in the huntingtin protein (Htt). Based upon non-clinical and clinical evidence, mHTT protein is considered the primary driver of HD pathophysiology [1]. Individuals who carry at least 40 CAG repeats inevitably experience progressive motor, cognitive, and functional decline, usually in adult life, with a mean age of motor onset of 45 years. The average illness course post-motor onset is approximately 10 to 20 years, with pneumonia, heart failure, or other complications frequently cited as the cause of death [2].

2. STUDY DESIGN

Eligible subjects will receive dose assigned to the cohort they are allocated to. Three dose levels are tentatively planned as follows:

- Dose level 1: 120 mg RO7234292 (n=4 patients)
- Dose level 2: 60 mg RO7234292 (n=4 patients)
- Dose level 3: 30 mg RO7234292 (n=4 patients)

This is not a randomization study. Patients are allocated to a cohort and hereby dose level according to the way they are sequentially enrolled into the study. Thus, the first 4 subjects will be assigned to 120mg, the next 4 subjects to 60mg and the next 4 subjects to 90mg.

After a review of medical data from the initial 3 dose levels and initial set of patients, a decision will be made whether to enroll additional patients and, in this case, whether to repeat a dose level, or to evaluate a lower or intermediate dose levels. The final number of dose levels and total number of patients assigned to a given dose level will be defined during the study. Up to a maximum of 20 patients will be enrolled in the whole study and the highest tested RO7234292 dose in this study will not exceed 120 mg, which is the highest test dose in the previous Phase I/IIa clinical study (ISIS 443139-CS1).

Study day is calculated relative to the date of first dose administration in Study BP40410. Study Day 1 will be the first treatment dose administration date. There is no day zero, hence the study day for patients who took at least one dose will be computed as follows:

Study Day = assessment date – treatment start date + 1,

if the assessment date is on or after the treatment date; or

Study Day = assessment date – treatment start date,

if the assessment date is earlier than the treatment date.

The end of this study is defined as the date when the last patient, last visit occurs. The end of the study is expected to occur approximately 6 months after the last study drug administration for the last patient has occurred. The total length of the study, from screening of the first patient to the end of the study, is expected to be approximately 1.5 years.

After completing study treatment in the current study, the patient will be eligible to enroll in an open label extension (OLE) study (BN40955) with active RO7234292 compound, provided the data from the ongoing RO7234292 program support continued development, the patient meets the inclusion and exclusion criteria for the OLE, and the OLE meets approval by the relevant competent authorities, IRBs, and ECs.

The SAP language supersedes the language in the protocol and protocol synopsis.

A schematic overview of the study design is presented in [Figure 1](#). For additional details, refer to the Schedule of Assessments in the study protocol (Appendices 1 and 2).

Screening	Treatment Period					Follow-up	
	In-House Periods		Out-Patient Visits				
Day -28 to Day -3	Day -2 to Day 4*	Day 28 to Day 29*	Day 30	Day 43	Day 71	Day 127	6 months (± 2 weeks) after last study drug administration
	
 1st dose of study drug on Day 1 CSF sampling from predose to 48 hours postdose 	
 2nd dose of study drug on Day 29 Single predose CSF sample on Day 29 	
 Single (equivalent to predose) CSF sample on Day 43, Day 71, Day 127, and FU 				

* Note: Patients will be admitted to the site in the afternoon/evening of Day -2 or in the morning of Day-1 to begin the first in-house period of the study; patients will be discharged on Day 4 after all assessments have been completed. Patients will return to the site for the second in-house period in the afternoon/evening of Day 28 or in the morning on Day 29 and will be discharged on Day 29 after all assessments have been completed.

CSF=cerebrospinal fluid; FU=follow-up.

Figure 1. Diagram of study design

2.1 OBJECTIVES

This study will evaluate the PK, PD, and safety of RO7234292 in patients with HD.

2.1.1 Primary Objectives

- To characterize the PK of RO7234292 in CSF and plasma following administration of multiple (2) IT doses of RO7234292
- To characterize mHTT CSF protein time course following administration of multiple (2) IT doses of RO7234292 in patients with HD
- To investigate the PK/PD relationship of multiple (2) IT doses of RO7234292 on mHTT in CSF

2.1.2 Secondary Objectives

- To assess the safety and tolerability of multiple (2) IT doses of RO7234292 in patients with HD
- To evaluate the immunogenicity of RO7234292
- To characterize the PK of RO7234292 in urine following administration of an IT dose of RO7234292

2.2 EXPLORATORY OBJECTIVES/ENDPOINTS

The exploratory objectives for this study would be to evaluate the effects of RO7234292 compared on the basis of the following endpoints:

- Change from baseline in exploratory biomarkers in CSF (e.g. neurofilament light chain [NfL])
- Relationship between exploratory fluid biomarkers in CSF and blood (e.g. CSF and plasma NfL)
- Relationship between biomarkers, safety (including Holter monitoring), PK, and immunogenicity
- Relationship of biomarkers to clinical severity at baseline using the UHDRS and Clinical Global Impression

Safety, PK, PD and clinical individual endpoints are outlined in the following sub-sections.

2.3 ENDPOINTS

2.3.1 Safety and Tolerability Endpoints

- Adverse events (AEs)
- Vital signs
- Electrocardiograms (ECGs)
- Clinical laboratory results
- Columbia - Suicide Severity Rating Scale (C-SSRS)
- Anti-drug antibodies (ADAs)

2.3.2 Pharmacokinetic Endpoints

PK parameters will be read directly from the (plasma, CSF) concentration-time profiles or calculated using standard non-compartmental methods. These parameters include but not limited to:

- Time to maximum (or peak) plasma concentration, maximum (or peak) plasma concentration
- Area under the plasma concentration-time curve (AUC) from time zero to the last measurable concentration, AUC from time zero to a timepoint, AUC from time zero to infinity, extrapolated AUC, AUC for a dosing interval
- Lambda(z), half-life; apparent total clearance
- Cumulative amount of unchanged drug excreted in urine, fraction of IT administered drug excreted in urine, renal clearance of the drug from plasma

2.3.3 Pharmacodynamic and Clinical Outcomes

• Biomarkers

- CSF levels, including but not limited to:
 - mHtt
 - NfL
- Plasma NfL
- MRI

- **Clinical-Reported Outcomes**
 - Montreal Cognitive Assessment (MoCA)
 - Huntington's Disease Daily Activities Scale (HD-DAS)
 - Independence Scale (IS)
 - Total Motor Scale (TMS)
 - Total Functional Capacity Scale (TFC)
 - Clinical Global Impression-Severity (CGI-S)
 - Clinical Global Impression-Change (CGI-C)
 - Symbol Digit Modalities Test (SDMT)
 - Stroop Wording Reading Test (SWRT)

2.4 DETERMINATION OF SAMPLE SIZE

Up to 20 patients with HD may be enrolled in this study. Due to the exploratory nature of this study, the actual number of patients will be determined during the study.

The sample size of 20 patients (at maximum) has been selected based on prior experience with second generation 2 ASOs given by IT injection to ensure that the PK and PD will be adequately assessed while minimizing patient exposure. The number of patients may be adapted during the study to sufficiently characterize the PK/PD relationship in CSF of RO7234292, while not exceeding 20.

2.5 ANALYSIS TIMING

Despite the tentative safety analyses performed in order to determine the subsequent dose levels, the final analysis will be conducted once all recruited patients have completed the study as defined in the protocol or withdrawn early from the study and data have been cleaned and verified and the database has been locked.

Given the adaptive nature of this study, data may be reviewed at any time by the Sponsor, to inform the decision of eventually enrolling more than the initial planned 12 patients.

Additionally, data may be used before the final analysis to support interactions with health authorities (HA).

3. STUDY CONDUCT

The Guidelines of the World Medical Association Declaration of Helsinki dated October 2002, the applicable regulations and guidelines of current Good Clinical Practice (GCP) as well as the demands of national drug and data protection laws and other applicable regulatory requirements will be strictly followed.

3.1 PATIENT ENROLLMENT

This is a non-randomization study as patients are assigned to a dose level in the order they are enrolled after successfully completing all screening evaluations and after the Investigator has verified that the patient is eligible per inclusion and exclusion criteria outlined in the Protocol.

In the event of a screen-failure, a maximum of 1 re-screening will be allowed within 4 weeks of the initial screening failure (e.g., as a consequence of abnormal laboratory values or general medical status not meeting inclusion or exclusion criteria). If re-screening is required, CAG repeat length testing does not need to be repeated (historical values will not be accepted), MRI and viral serology from the initial screening may be acceptable as part of the re-screening assessments, if performed within 4 weeks of the baseline visit.

4. STATISTICAL METHODS

Descriptive summary statistics including but not limited to n, mean, median, standard deviation, range (minimum, maximum) for continuous variables, and counts and percentages for categorical variables will be used to summarize data by dose level and visit. Where applicable, statistical tests will be conducted using 2-sided tests and 95% confidence intervals will be reported.

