4.1 ANALYSIS POPULATIONS

4.1.1 Safety Population

All patients who are enrolled and received any dose of RO7234292, whether prematurely withdrawn from the study or not, will be included in the safety analyses.

The Safety Population will be the primary population for all safety analyses and patients will be analyzed by dose received.

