4.1.4 Pharmacodynamic Population

All patients who are enrolled and receive at least 1 dose of RO7234292, have not significantly deviated from the protocol, violated inclusion or exclusion criteria. Patients with incomplete data may be excluded if this would undermine the interpretability of the PD analysis. Excluded cases will be documented together with the reason for exclusion.

4.2 **BASELINE DEFINITIONS**

For all assessments, baseline will be defined as the last non-missing measure prior to the first dose administration. For fluid biomarkers, if appropriate time-matched baseline may also be considered to assess diurnal effects.

4.3 **ANALYSIS OF STUDY CONDUCT**

The number of patients who enroll in the study, discontinue from the study, and complete the study will be summarized overall and by dose level. Reasons for premature study withdrawal will be listed and summarized. All major protocol deviations will be listed and summarized.

Additional analyses will be performed to assess and describe the impact of COVID-19 on the study conduct.

4.4 **ANALYSIS OF TREATMENT GROUP COMPARABILITY**

Demographic and baseline characteristics will be summarized by dose level using but not limited to n, mean, standard deviation, median and range for continuous variables and proportion for categorical variables, as appropriate. Summaries will be presented overall and by dose level.

4.5 **DATA HANDLING RULES**

For safety laboratory and measurements that are reported as ' $<x$ ' or ' $>x$ ', the analysis value will be replaced by 'x'. For biomarkers (e.g. CSF mHtt, CSF NfL, etc) where entries will be indicated as 'BLQ', the analysis value will be set to BLQ divided by 2 (BLQ*0.5). No imputation will be performed on missing entries without a corresponding BLQ limit. In case of listing, however, the original data entries will be presented.

A summary table for subjects with imputed values by dose level and visit will be presented for each parameter.

For CSF/plasma biomarkers (e.g. NfL, mHtt) and CSF protein, scatter plots to assess relationships will be based on the natural log-transformed parameter.

For PK concentrations, BLQ values will be set to zero if corresponding time was prior to Tmax and set to missing after Tmax.

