4.7.2 Adverse Events

All treatment-emergent adverse events (TEAEs) and serious adverse events (SAEs) will be summarized for each dose level and for all patients using the Medical Dictionary for Regulatory Activities (MedDRA) coding by system organ class, preferred term, relationship to Study Drug, and severity. Missing data will be handled as described in Section 4.6. Percentages presented in AE tables will display the percentage of patients within a treatment dose level experiencing the AE at least once.

For frequency counts by preferred term, multiple occurrences of the same AE in an individual are counted only once. For overall total number of events, multiple occurrences of the same AE in an individual are counted separately.

An adverse event will be regarded as treatment emergent adverse event (TEAE) if the event occurs after the first dose of treatment or worsened after treatment.

Adverse events that occur before first dose administration and are not related to study procedure will be included in data listings only. SAEs and non-serious AEs that lead to treatment discontinuation or treatment interruption will be listed separately. Selected AEs, for instance procedure related AEs, will be summarized and listed separately.

Additional analyses will be considered to describe the impact of COVID-19 on patient safety.

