4.7.3 Laboratory Data

Laboratory data including chemistry, hematology, CSF safety labs and urinalysis, will be collected throughout the study.

Summary statistics at each assessment time will be presented using the International System of Units (SI units; Système International d'Unités). Laboratory data not reported in SI units will be converted to SI units before processing.

Descriptive tables will be used to summarize absolute, change and percentage change from baseline by dose level and study day. Measurements reported as ' $>x$ ' or ' $<x$ ' will be handled as outlined in Section [4.5](#).

Spaghetti plots (with overlaid median) for absolute and change and percentage change from baseline values will be presented for all parameters by dose level on the numeric time scale.

In addition, the shifts (relative to the normal range) from baseline to the minimum and maximum post-baseline values will be presented. If a subject is missing a baseline value but had a post-baseline value, then the baseline assessment is labeled as "unknown". Likewise, if a subject had a baseline value but had no post-baseline values, then the minimum and maximum are labeled as "unknown". For each parameter, the incidence of shift to *low* (below the normal range) will be summarized using the minimum post-baseline values; the incidence of shift to *high* (above the normal range) will be summarized using the maximum post-baseline values.

Finally, the number of patients with abnormal absolute values for the CSF safety labs, according to the parameter ranges presented in [Table 1](#) will be summarized by dose level and visit and also as a listing. Red blood and white blood counts cannot be negative and the lower normal range limit is 0, hence no abnormal low values. Roche standard reference ranges, rather than the reference ranges of the Investigator will be used for all parameters.

For most parameters, the measured laboratory test result will be assessed directly using the Roche standard reference range. Certain laboratory parameters will be transformed to Roche's standard reference ranges. A transformation will be performed on certain laboratory tests that lack sufficiently common procedures and have a wide range of Investigator ranges, e.g., enzyme tests that include AST, ALT, alkaline phosphatase, and total bilirubin. Since the standard reference ranges for these parameters have a lower limit of zero, only the upper limits of the ranges will be used in transforming the data.

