4.8.1 Describing Parameters over Time

All clinical outcomes will only be collected at Screening and follow-up visits, hence, descriptive tables (Table 5) will be presented at these two visits (including change from baseline at follow-up visit), while association analysis (Table 6) involving these parameters will only be presented at baseline.

As presented in Table 5, for PD biomarkers, descriptive tables will be presented per each time point and dose level. Additionally, for biomarkers, spaghetti plots (with overlaid median) for absolute, change and percent change from baseline values using untransformed data will be presented for all parameters by treatment dose level. In addition, individual patient profiles for selected biomarkers on absolute, change and percent change from baseline will be presented on the same page.

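### In the planned 12 patients, catheter regimen very likely coincides with dose for 120 mg versus dose level 3, and the SAP's by-dose AE and CSF-safety displays do not show which regimen a patient had

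*SAP*

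**What the plan says.** **Allocation.** Protocol 4.2 and SAP Section 2 assign dose by order of enrolment: four patients to 120 mg, four to 60 mg, then four to dose level 3. There is no randomisation.

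**Catheter.** Protocol 5.1.1.4 records two lumbar abscesses among six patients of this study whose catheter stayed in for 4 days. Protocol 1.3 and 4.5.5 now have the catheter removed 48 hours after the first dose. Section 4.5.5 also requires MRSA swabs (with decolonisation if positive), antibacterial washing, daily CSF safety testing during the dwell, and culture of the catheter tip. SAP Figure 1 already shows the 48-hour schedule.

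**Displays.** The general rule in SAP Section 4 is that "counts and percentages for categorical variables will be used to summarize data by dose level and visit". For safety, SAP 4.1.1 adds that "patients will be analyzed by dose received". SAP 4.7.2 says "All treatment-emergent adverse events (TEAEs) and serious adverse events (SAEs) will be summarized for each dose level", and also that "Selected AEs, for instance procedure related AEs, will be summarized and listed separately". In SAP 4.7.3, abnormal CSF safety values "will be summarized by dose level and visit and also as a listing". Protocol 6.4 promises AE incidence by attribution to drug or procedure. The SAP mentions neither catheter duration nor the change of regimen. COVID-19 is the only mid-study change for which it plans extra analyses.

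**Dose level 3.** SAP Section 2 lists it as 30 mg, but its allocation sentence sends the third group of four to 90 mg. The same section says that the SAP takes precedence over the protocol.

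**The concern.** When dose follows enrolment order, any mid-study change of procedure falls unevenly on the dose groups. Here the change concerns the catheter, which is the suspected source of the most notable safety finding so far. A table with columns for dose and no marker for regimen can show catheter events as a pattern across doses.

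CSF safety results have the same weakness. Protocol 5.1.2.2 lists rises in CSF white cells and protein as a potential drug risk. A rise caused by the catheter or by infection would look the same in a by-dose table.

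The displays also feed decisions. Protocol 3.1 and 4.3.2 use safety, laboratory, PK and biomarker data to decide which doses to repeat or add. SAP 2.5 and 4.10 allow the sponsor to look at the data at any time and to use them with health authorities.

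**Working it through.** **Inputs**
- Planned patients: 3 dose levels × 4 = 12, which matches the initial 12 in SAP 2.5.
- Order: patients 1–4 at 120 mg, 5–8 at 60 mg, 9–12 at dose level 3 (SAP Section 2).
- Earlier regimen: 6 patients, 2 with an abscess (Protocol 5.1.1.4).
- Assumption: the six are enrolment numbers 1–6. The documents do not say so. They also do not say whether a seventh or eighth patient had the longer catheter, so 7 and 8 are shown as a range.

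**Step 1: regimen by dose.** Patients on the earlier regimen:

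| Total on earlier regimen | 120 mg | 60 mg | Dose level 3 |
|---|---|---|---|
| 6 | 4/4 | 2/4 | 0/4 |
| 7 | 4/4 | 3/4 | 0/4 |
| 8 | 4/4 | 4/4 | 0/4 |

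The outer columns are the same in every row. They stay the same whenever the first patient on the new regimen is any of numbers 5 to 9.

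**Step 2: the direct contrast.** Among the 120 mg and dose level 3 patients alone, the regimen indicator equals the 120 mg indicator. The design (two dose columns plus regimen) has rank 2 of 3, so the two effects are completely aliased.

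**Step 3: what 60 mg can add.** Take a continuous measure with variance σ² and an additive model without interaction.
- Unadjusted 120 mg vs dose level 3: σ²/4 + σ²/4 = 0.5σ².
- Regimen effect from 60 mg, 2 vs 2: σ²/2 + σ²/2 = σ².
- Adjusted contrast: 0.5σ² + σ² = 1.5σ². The standard error rises by √(1.5/0.5) = 1.73.
- With a 3 vs 1 split: 0.5σ² + (1/3 + 1)σ² = 1.83σ², a factor of 1.91. With 4 vs 0, the contrast cannot be estimated.

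**Step 4: the abscesses by dose.** Two events among six patients (four at 120 mg, two at 60 mg) can be placed in C(6,2) = 15 ways: both at 120 mg in C(4,2) = 6, one at each dose in 4 × 2 = 8, both at 60 mg in 1. The table would then read 2/4 and 0/4, 1/4 and 1/4, or 0/4 and 2/4. Neither event can fall at dose level 3.

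**Step 5: the abscesses by regimen.** 2/6 = 33%, Clopper-Pearson 95% CI 4.3% to 77.7%. If the later six patients had none (an assumption), Fisher's exact two-sided p for 2/6 vs 0/6 is 2 × 15/66 = 0.45. A test by regimen would therefore settle nothing.

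**The case against.** The strongest reply is that little is damaged. The study is descriptive, its sample size has no formal basis, and no dose-comparison test is specified. The protocol already reports the abscesses as a catheter risk, so an informed reader would hardly take them for a dose effect. Procedure-related events get their own summary, attribution to procedure is tabulated, and CSF abnormalities are listed. With 12 patients the regimen could be worked out by hand. A split by catheter duration is itself confounded with dose and with the added infection measures.

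Much of this stands. It limits the point to interpretation and rules out a test. It does not remove the point: none of those displays says which regimen a patient had, procedure attribution rests on the investigator's judgement, and CSF white cell or protein values carry no attribution at all.

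A reader might infer more than the documents support:
- **Distorted CSF biomarkers.** SAP 4.8.1 does say that "for PD biomarkers, descriptive tables will be presented per each time point and dose level", but no figure in the documents shows a catheter effect on mHTT or NfL. The optional baseline in SAP 4.2 ("For fluid biomarkers, if appropriate time-matched baseline may also be considered to assess diurnal effects") is offered for diurnal effects, not as a remedy for regimen.
- **More abnormal values from more sampling.** Shifts to high values "will be summarized using the maximum post-baseline values", so the number of samples could matter. The earlier CSF safety schedule is not in the documents, so there is no comparator.
- **Protocol version as a stand-in for regimen.** Protocol 9.6 lets changes that remove an immediate hazard start before approval, so the two need not coincide.

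**Conclusion.** The concern holds for the AE and CSF-safety displays. In the planned 12, catheter regimen is aliased with dose for 120 mg versus dose level 3, most likely as 4/4, 2/4 and 0/4 on the earlier regimen. The existing procedure-related summaries mitigate this only in part.

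Two assumptions carry it: that the six patients were the first enrolled, and that the new regimen was in force by patient 9. The exact split at 60 mg does not matter for the outer contrast. Up to 20 − 12 = 8 further patients could reduce the aliasing, depending on the doses chosen, but the plan cannot rely on that.

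A reader might conclude that catheter duration caused the abscesses, or that a planned inference is invalid. The documents support neither. Duration changed together with the infection and monitoring measures, and there is no formal dose comparison to invalidate. Severity is minor to moderate.

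The conflict between 30 mg and 90 mg in SAP Section 2 is a separate and certain error in a document that overrides the protocol.

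**What to change.** In the SAP:
1. Derive actual catheter duration from the recorded insertion and removal, both scheduled events in Protocol Appendix 1, and flag it in the AE and CSF-safety listings. Use actual duration, not protocol version.
2. Tabulate procedure- or catheter-related AEs and abnormal CSF safety values by dose and actual catheter duration, as counts only and without a test.
3. State three limitations: 120 mg versus dose level 3 cannot be separated from regimen in the planned 12; infection and monitoring measures changed as well; and the split by duration is itself confounded with dose except within the 60 mg group.
4. Reconcile the dose list with the allocation sentence in Section 2.

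The cost is SAP wording, one derived variable and a few small tables, with no new data or visits. The downside is that the within-dose comparison is at best 2 vs 2 and may not exist, and the reported dose contrast becomes more qualified.
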